# 3. STUDY PURPOSE

An ankle replacement procedure consists of replacing the worn-out joint surfaces of the ankle with metal and plastic components that are shaped to allow continued movement of the ankle. There are several different types of ankle replacement available. Infinity ankle implants are already routinely used in NHS hospitals. The INFINITY™ with ADAPTIS™ and EVERLAST™ ankle replacement system is a development of the Infinity ankle implant, designed to attach to the bone better and to wear out more slowly.

The purpose of the UK ADAPTIS™ Study is to assess the performance and function of the newly introduced INFINITY™ with ADAPTIS™ and EVERLAST™ technology Total Ankle System for total ankle replacement (TAR) or arthroplasty (TAA) and EVERLAST™ Poly Insert that modernises and streamlines Stryker's TAA/TAR portfolio.

### 4. STUDY DESIGN

This is a prospective multi-centre cohort study of INFINITY™ with ADAPTIS™ and EVERLAST™ technology Total Ankle System TAA/TAR implantations.

Patients meeting the criteria for the study will be invited to enrol by providing written (electronic) informed consent.

The patients will be monitored clinically by post-operative follow-up examinations and patient reported outcome measures (PROMs).

The length of the Patient follow-up schedule in the study is based on the previously published UK INFINITY™ Study¹.

The study is set up to record data pre-operative, intra-operative, and at 6 weeks, 6 months, 1 year, 2 years, and 5 years post-operative.

# 5. OBJECTIVES AND OUTCOMES

#### **5.1 PRIMARY OBJECTIVE**

The primary objectives of the study are to assess device survivorship and performance using rates of re-operation/revision and functional status (MOXFQ) over a 5-year post-operative period.

### **5.2 PRIMARY OUTCOMES**

Primary outcomes are functional status (MOXFQ) at 2-year post-operative and device survivorship at 2 years.

### **5.3 SECONDARY OUTCOMES**

Secondary outcomes are:

- 1. Survivorship as removal or exchange of one or more of the components (excluding incidental polyethylene exchange for infection) at 2 years, 5 years and post-operative.
  - a. Revision of any components (excluding incidental polyethelene exchange for infection).
  - b. Re-operation without revision
  - c. Type and frequency of adverse events (AEs), specifically operative and device related AEs and Serious AEs (SAEs).
- 2. Functional status, pain and disability (MOXFQ & AOS) and health-related quality of life (EQ5D-5L) at 6 months, 1 year, 2 years, and 5 years post-operative.
- 3. Clinical assessment 6 weeks, 6 months, 1 year, 2 years, and 5 years postoperative.
- 4. Radiographic assessments at 6 months 1 year, 2 years, and 5 years postoperative.

### 6. PATIENT SELECTION

### **6.1 SAMPLE SIZE**

This study will collect data on a minimum of 200 patients implanted with the of INFINITY™ with ADAPTIS™ and EVERLAST™ technology Total Ankle System for a TAA/TAR. A minimum of 200 patients recruited has been stipulated to accommodate any participants that withdraw from the study, ensuring a sufficient sample size is achieved.

#### **6.2 ELIGIBILITY**

The following inclusion and exclusion criteria will be used to distinguish patients eligible for enrolment into this study. Eligibility will be confirmed by the patient's treating clinician.

## **6.2.1 INCLUSION CRITERIA**

- Male or non-pregnant female over 21 years of age with a diagnosis of end stage ankle arthritis and requiring primary TAA/TAR and is suitable for the use for the INFINITY™ with ADAPTIS™ and EVERLAST™ technology Total Ankle System.
  - a. If a female participant of child-bearing age becomes pregnant prior to surgery/after study consent, their surgery will be deferred as standard care and therefore will be withdrawn from the study.
  - b. If a female participant of child-bearing age becomes pregnant during the post-operative follow-up periods, radiographic assessments are likely to still be appropriate. Local radiation protection procedure should be followed. If a pregnant participant elects not to have radiographs, other clinical assessment and PROMs data can still be recorded and they do not need to be withdrawn from the study.
- 2. Patients who are physically and mentally willing and able to comply with the post-operative follow-ups and an appropriate rehabilitation schedule.
- 3. Patient can understand and provide written consent.

### **6.2.2 EXCLUSION CRITERIA**

- 1. Patients with previous ankle arthrodesis or patients who require revision of previously implanted TAA/TAR.
- 2. Any patients presenting with clinically relevant conditions prior to implantation, that would contraindicate implantation of a TAA/TAR.

### **6.3 PATIENT SCREENING**

Patients will primarily be screened from theatre lists of patients waiting for a TAA/TAR and are eligible to receive the INFINITY™ with ADAPTIS™ and EVERLAST™ technology Total Ankle System for TAA/TAR as part of their routine

care. This will be done by a designated clinician, healthcare professional or delegated member of the research delivery team.

Patients may also be screened from orthopaedic outpatient clinics where patients have been referred through standard practice. Members of the healthcare team will screen for eligible patients and have their eligibility confirmed by their treating clinician.

All patients that have been screened will need an eligibility form completing on REDCap (Research Electronic Data Capture). For those that are eligible, a delegated member of the research delivery team will also complete a contact details form.

Potentially eligible patients will be contacted by a delegated member of the research delivery team, they will be provided a patient information sheet (PIS) in person, via their email or via post depending on patient preference. If a patient is interested, consent will be collected (a) electronically via REDCap (in person or via a link sent); (b) written consent (in person or via post) and uploaded to REDCap; (c) verbal consent which will be documented on REDCap – this will need to be followed up by either electronic or written consent. Consent will include future linkage to National Joint Registry (NJR) data and collection of radiographs for future analysis. An agreement in principle will be sought from NJR for future data access.

Each site will keep an electronic screening log, documenting the date of screening, results of screening and the primary reason for excluding a patient or reason a patient has decided not to participate as available. The screening log will be held on the secure database REDCap as hosted by the study management team at South Tees Hospitals NHS Foundation Trust.

## **6.4 PARTICIPANT IDENTIFIER**

Each patient screened will be allocated a unique participant identifier. For those patients recruited, the unique participant identifier will be used for the duration of the study. The local research delivery team will maintain a confidential participant identification log, local patient identifiers and patient names with the corresponding unique participant identifier. This will enable records to be identified locally.

### 6.5 DISCONTINUATION AND WITHDRAWAL

Patients are free to withdraw from the study at any time and are under no obligation to provide a reason for doing so. Though, all attempts should be made to record the reason why the patient withdrew, this will be captured within the "Discontinuation and Withdrawal" form within REDCap.

If the patient fails to attend scheduled follow-up clinical appointments or respond to telephone calls to collect PROMs, every effort will be made to contact the patient to assess their health status. The local research delivery team should attempt to contact the patient through 3 documented attempts (phone calls, letter or email) on REDCap. The visit will be classed as "missed" if they do not respond. The local research delivery team should continue to attempt contacts for future scheduled follow-up appointments and assessments.

The patient may also be discontinued or withdrawn from the study if in the local Principal Investigator's (PI) or CI's opinion, continuation in the study would be detrimental to the patient's health and wellbeing.

Withdrawing or discontinuing from the study will not affect the patient's accessibility or quality of medical care.

Patients who withdraw or are discontinued will keep their unique participant identifier. The information that has already been collected from the patient will be included in the database and final analyses. The patient will continue to have their hospital information collected unless the patient withdraws their initial consent for this, this will be confirmed with the patient at the point they request to be withdrawn. PROMs data collection will cease at the point the patient withdraws or is discontinued from the study.

### 7. RISK-BENEFIT ANALYSIS

#### 7.1 RISKS

All Patients in this study will undergo a TAA/TAR according to standard health care.

The potential risks for a TAA/TAR in general are:

- 1. Aseptic loosening of the prosthesis
- 2. Infection
- 3. Deep venous thrombosis
- 4. Post-operative pain
- 5. Heterotopic ossification
- 6. Fracture of the prosthesis
- 7. Fracture of the bone
- 8. Loss of muscle force
- 9. Nerve and vessel injury
- 10. Wound healing problems
- 11. Implant failure
- 12. Medical complications

13. Death

### 7.2 BENEFITS

The potential benefits for a TAA/TAR in general are:

- 1. Pain reduction
- 2. Increased function
- 3. Improved quality of life

The potential benefits for the INFINITY™ with ADAPTIS™ and EVERLAST™ technology Total Ankle System include:

- 1. Bony integration of the metallic components
- 2. Reduced pain
- 3. Restored alignment
- 4. Replacement of flexion and extension movement in the ankle

#### 7.3 RADIATION

Radiographic assessment of the ankle will be at baseline and at 6 months, 1 year, 2 years and 5 years post-operatively.

### 8. DEVICE DESCRIPTION

The INFINITY™ with ADAPTIS™ and EVERLAST™ technology Total Ankle System is a two-piece semi-constrained fixed-bearing, bone-sparing total ankle prosthesis that restores mobility to a failing ankle joint. The System consists of a highly polished metal talar dome, a titanium alloy tibial tray, and Poly Insert (an ultra-high molecular weight polyethylene tibial insert). The components are available in a variety of sizes and design configurations intended for both primary and revision applications.

Through the advancement of partial and total joint replacement implants, the surgeon has been provided with a means of restoring mobility, correcting deformity, and reducing pain for man patients. While the prostheses used are largely successful in attaining these goals, it must be recognised that they are manufactured from a variety of materials and that any joint replacement system, therefore, cannot be expected to withstand activity levels and loads as would normal healthy bone. In addition, the system, including the implant/bone interface, will not be as strong, reliable, or durable as a natural human joint.

This system is manufactured according to International Conference on Harmonisation (ICH) Good Clinical Practices (GCP) in accordance with applicable Good Manufacturing Practices (GMP) and ISO 14155:2020 through relevant manufacturing and related validation processes.

The INFINITY™ with ADAPTIS™ and EVERLAST™ technology Total Ankle System Tibia Tray and Talar Dome are manufactured using an improved process known as Direct Metal Laser Sintering, also known as ADAPTIS™ 3D printing, produces a porous metal surface made from Ti6Al4V (Tibia Tray) and CoCr (Talar Dome), respectively, to interface with the bone.

The INFINITY™ with ADAPTIS™ Technology modular articular inserts are manufactured from EVERLAST™ Highly Crosslinked Polyethylene blended with Vitamin E. The propriety manufacturing process has been optimised to develop an enhanced ankle insert with retained material strength, reduced oxidation potential, and improved wear resistance. They are available in 8 sizes, with 4 thicknesses per size.

The INFINITY™ with ADAPTIS™ and EVERLAST™ technology Total Ankle System includes:

- INFINITY™ with ADAPTIS™ Technology Tibial Tray
- INFINITY™ with ADAPTIS™ Technology Chamfer-Cut Talar Component
- INFINITY™ with ADAPTIS™ Technology Flat Cut Talar Dome
- INFINITY™ EVERLAST™ Poly Insert

### 9. CASE REPORT FORMS

Patients will be screened for eligibility and assessed pre-operatively, intraoperatively, and post-operatively at 6 weeks, 6 months, 1 year, 2 years, and 5 years.

### 9.1 DATA COLLECTION

The study data/case report forms (CRF) will be collected and managed using REDCap electronic data capture tools, hosted at South Tees Hospital NHS Foundation Trust. REDCap is a secure, web-based software platform designed to support data capture for research studies, providing (1) an intuitive interface for validated data capture; (2) audit trails for tracking data manipulation and export procedures; (3) automated export procedures for seamless data downloads to common statistical packages; (4) procedures for data integration and interoperability with external sources.

### 9.1.1 SCREENING AND ELIGIBILITY

- 1. Screening
- 2. Inclusion and exclusion criteria
- 3. Contact details

# **9.1.2 CONSENT**

- Electronic consent (email)
- Written consent (face to face or postal)
- Verbal consent (telephone)

### 9.1.3 PRE-OPERATIVE CLINICAL HISTORY

- 1. Date of birth
- 2. Weight
- 3. Height
- 4. Sex
- 5. Indication for implantation
  - a. Primary osteoarthritis
  - b. Post-traumatic arthritis without previous fracture
  - c. Post-traumatic arthritis with previous fracture
  - d. Previous ankle surgery (non-trauma related)
  - e. Inflammatory arthritis
  - f. Other (please specify)
- 6. Previous surgery to the ankle planned for operation
  - a. Yes
  - b. No
- 7. Co-existing diseases
  - a. Allergies
  - b. High blood pressure
  - c. Previous history of VTE events (Blood Clot, Thrombosis, Embolism etc.)
  - d. Ischaemic Heart Disease or previous MI
  - e. Rheumatic fever, heart murmur
  - f. Pacemaker
  - g. Heart arrythmias

- h. COPD
- i. Asthma, bronchitis, emphysema
- j. Arthritis, muscle disease
- k. Liver disease, jaundice
- Thyroid disease
- m. Diabetes
- n. Kidney disease
- o. Other (please specify)
- 8. Radiographs
  - a. Date of radiograph
  - b. Date of repeat radiograph
- 9. Surgeon completed radiographic report

Usual standard of care pre-operative radiographs will include a standing AP and lateral film of the ankle. Adjacent joint arthritis may be assessed by CT if usual surgeon preference but, not required for this study.

- a. Canadian Orthopaedic Foot and Ankle Society (COFAS) grade
  - i. Type 1 = Isolated ankle arthritis
  - ii. Type 2 = Ankle arthritis with intra-articular varus or valgus deformity.
    - Defined as a coronal plane deformity of more than 10 degrees
  - iii. Type 3 = Ankle arthritis with hindfoot deformity, tibial malunion, midfoot ab-or adductus, supinated midfoot, plantar-flexed first ray, etc

Hindfoot deformity defined as the angle between the lateral border of the calcaneus and the long axis of the tibia on the AP view of the ankle (varus more than 5 degrees, valgus more than 10 degrees).

Tibial deformity defined as an angulation between the lateral border of the tibia more than 10 degrees on the AP view of the ankle.

- iv. Type 4 = Types 1-3 plus subtalar, calcaneocuboid, or talonavaciular arthritis.
  - Arthritis assessed either by plain radiograph or clinical evaluation
- b. Coronal plane deformity (Midline Tibio Talar Angle MTTA)

  Measured in degrees as the angle between a line perpendicular to the anatomical axis of the tibia and a line drawn along the top of the talar dome (see, Figure 1).
  - i. Degrees
  - ii. Varus or valgus

Figure 1: MTTA

# 9.1.4 PRE-OPERATIVE PROMS

- 1. Date completed
- 2. MOXFQ
- 3. AOS
- 4. EQ5D-5L

# 9.1.5 INTRA-OPERATIVE EVALUATION

- 1. Surgery date
- 2. Operative side
  - a. Left
  - b. Right
- 3. Anaesthesia Class and Type
  - a. General
  - b. Regional, Epidural
  - c. Regional, Nerve Block
  - d. Regional, Spinal
  - e. Other
- 4. Duration of surgery
  - a. Hours/Mins
- 5. Intra-operative AEs
  - a. Yes
    - i. Fracture
    - ii. Nerve or Vessel Injury
    - iii. other
  - b. No

- 6. Components used and sizes
- 7. Patient Specific or Standard Instrumentation (PSI)

### 9.1.6 POST-OPERATIVE CLINICAL HISTORY

- 1. Follow-up timepoint
  - a. 6 weeks
  - b. 6 months
  - c. 1 year
  - d. 2 years
  - e. 5 years
- 2. Date of assessment
- 3. Has the patient experienced any post-operative AE/SAEs
- 4. Radiograph (not required for 6 weeks)
  - a. CT

This data will be used if indicated as part of clinical care, and therefore it may not be available for all participants

- b. Plain radiograph
- c. Radiographic reporting template

  The purpose of the post-operative radiographic evaluations will be to assess, record, and report for migration, loosening, subsidence of the device, any osteolysis and cyst formation.

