# 2. EVALUATION SCHEDULE

Evaluation	*Pre- Op	Intra- Op	**6 weeks	6 months	1 year	2 years	5 Years
Time Window	N/A	N/A	+/- 2weeks	+/- 2weeks	+/- 6weeks	+/- 3months	+/- 6months
Inc./Exc. Criteria	Х						
Pre-Op Clinical History	X						
Intra-Op Surgical Details		Х					
Clinical Follow- Up			X	Х	X	x	х
MOXFQ	Х			Х	Х	Х	Х
AOS	Х			X	X	X	Х
EQ5D-5L	Х			Х	Х	Х	X
Radiographs	Х			Х	Х	Х	Х
Adverse Events or Termination	Anytime						

\*Pre-Op: Date of or any time post the date of written informed consent up to 6 months prior to date of surgery.

If Patients exceed a 6 month wait for surgery, a radiograph will be repeated at their pre-operative assessment or on the morning of surgery as part of routine care.

Patient study consent will be valid for the 12 months from the date of consent unless withdrawn.

\*\*6 Weeks: This is not an additional study-related clinical visit. Research teams will be required to review the 2- and 6-week clinical visits that occur as standard of care to report any adverse events.

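### Migration and subsidence are to be read from films, but the protocol requires no film of the implanted ankle before 6 months and names no early reference film

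*Protocol*

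**What the plan says.** Radiographic assessment is the fourth secondary outcome in Protocol section 5.3: "Radiographic assessments at 6 months 1 year, 2 years, and 5 years postoperative". Section 9.1.6 gives its content; the films are to "assess, record, and report for migration, loosening, subsidence of the device, any osteolysis and cyst formation".

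The timing is the same wherever imaging is mentioned. Section 7.3 states "Radiographic assessment of the ankle will be at baseline and at 6 months, 1 year, 2 years and 5 years post-operatively". The table in section 2 marks radiographs at the pre-operative, 6-month, 1-year, 2-year and 5-year columns and leaves the intra-operative and 6-week columns blank. The follow-up form in 9.1.6 covers the 6-week visit but carries the note "Radiograph (not required for 6 weeks)".

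Baseline here means a film of the native ankle. Section 9.1.3 describes it: "Usual standard of care pre-operative radiographs will include a standing AP and lateral film of the ankle". For a patient who waits more than 6 months, section 2 adds that "a radiograph will be repeated at their pre-operative assessment or on the morning of surgery as part of routine care", which is still before implantation.

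Section 3 describes the device as "designed to attach to the bone better and to wear out more slowly".

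**The concern.** Migration and subsidence cannot be read as change from a single image; two images of the implant in place are needed. The pre-operative film cannot be the first of the pair, because it shows no implant. Under the required schedule the first image that can serve is the 6-month film. Any settling before then is already part of that film's starting position, and the 1-, 2- and 5-year comparisons cannot show it.

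This matters because better attachment to bone is part of the stated rationale for the device, and bony integration heads its device-specific benefits in section 7.2. Movement in the first months bears directly on that. A descriptive report of little or no migration would leave the reader unsure whether it covered the time since surgery or only the time since 6 months.

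**Working it through.** The protocol states no figure for radiographic change, so there is none to reproduce. The check sets its imaging entries side by side and then works out the interval left without a required reference.

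**Step 1. Which required or specified images show the implant before 6 months?**

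| Protocol section | Entry | Shows the implant before 6 months? |
|---|---|---|
| 2, table | Radiograph pre-operatively, then from 6 months | No |
| 2, footnote on waits over 6 months | Repeat film before surgery | No |
| 2, footnote on 6 weeks | Routine 2- and 6-week visits reviewed for adverse events | No film requested |
| 7.3 | Baseline, then from 6 months | No |
| 9.1.5 | Seven intra-operative items; components recorded by type and size | No image listed |
| 9.1.6, plain film | Not required at 6 weeks | Possible, not required |
| 9.1.6, CT | Used if clinically indicated, may be unavailable | Possible, not systematic |

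Required films of the implanted ankle before the 6-month visit: 0. Early films designated as reference: 0.

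**Step 2. How long is the interval?**

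- The 6-month visit has a window of +/- 2 weeks (section 2).
- 6 months is about 26.1 weeks, so the first required film falls between 26.1 - 2 = 24.1 and 26.1 + 2 = 28.1 weeks, or roughly 5.5 to 6.5 months.
- As a share of the 24 months to the 2-year film: 5.5/24 = 23% and 6.5/24 = 27%.

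That share is a length of time only. It is not an amount of bias.

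**Step 3. What can later films measure?**

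Let p(t) be component position relative to bone at time t, however it is graded. Movement since surgery is p(t) - p(0). With the 6-month film as the only assured reference, what can be measured is p(t) - p(6 months). The difference between the two is p(6 months) - p(0), the early movement. It does not appear in any later comparison, whatever its size. The protocol gives no frequency or amount for it, so the understatement has a possible direction but no size that can be calculated.

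**Step 4. Which listed features are affected?**

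Of the five features in 9.1.6, migration and subsidence depend on a reference, and the gap concerns only the early interval. Osteolysis and cysts can be seen on a single film, and loosening may be. Change after 6 months is measurable as planned.

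**The case against.** A reader might infer that no early film is taken at all and that the 6-month reader has nothing to compare with. The documents do not support this. A film that is not required at 6 weeks is not forbidden. The radiograph item sits on a form whose first timepoint is 6 weeks, CT may be done where indicated, and consent under section 6.3 covers collecting radiographs for future analysis. Routine films may exist; the protocol does not say either way. What stands is that none is assured or named as the reference.

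A reader might also infer that early subsidence is lost altogether, including as an adverse event. That goes too far. Sites must "review the 2- and 6-week clinical visits that occur as standard of care" for adverse events. Section 10 requires all events to 90 days and ankle-related events after that, and section 10.1 lists subsidence as a category. Early subsidence recognised in care is therefore recorded whatever the film schedule. This route is incomplete only for silent movement.

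A third inference would be harm to the primary analysis. The primary outcomes in section 5.2 are MOXFQ and device survivorship at 2 years. Neither is derived from these films; section 5.3 describes survivorship by removal or exchange of components.

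Finally, the radiographic reporting template named in 9.1.6 is not shown and may already say how films are compared. That is a fair caution about the reading rule. But neither a template nor an analysis plan can recover an early film that was never collected, and what is collected is set by the schedule and forms in this protocol.

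**Conclusion.** The point holds in a limited form. The protocol makes migration and subsidence a purpose of its radiographic assessment, requires no film of the implanted ankle before about 24 to 28 weeks, and names no early reference. Early movement that is not recognised clinically may go unmeasured, and change at 1, 2 and 5 years is guaranteed only relative to 6 months.

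This rests on two assumptions: that migration and subsidence are meant as change in component position, and that the unseen template does not already call for an early film. How often routine early films exist at the sites is unknown. If nearly all patients have one, the practical gap is small once those films are collected; if few do, most results will describe change after 6 months. In either case this is a cheap improvement to a descriptive secondary outcome, with no bearing on the primary outcomes.

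**What to change.** In sections 9.1.5 and 9.1.6:

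- Ask sites to upload, with its date, any intra-operative or early post-operative radiograph already taken in routine care. No new imaging is requested.
- State that the earliest film showing the implant is the reference for migration and subsidence.
- Where no such film exists, use the 6-month film as reference, label the result *migration/subsidence after 6 months*, and report those patients separately from those with an early reference.

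The cost is one upload and date field and one sentence in the reporting template. Sites already look back at the 2- and 6-week visits, and consent already covers radiograph collection. The downside is that reference films will differ in date and weight-bearing status and will be missing for some patients, so the remedy is partial. Early films are easiest to gather prospectively.
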